5.2 Specific Aims 1-3

Compare effectiveness of financial incentive, environmental strategy, and combined arm to control during Phases I and II. For expected weight change between months 0-18 of -8 kg, -5 kg and 0 kg in the combined, intervention and control groups, respectively (a net difference between single intervention and control groups of 5 kg and between combined intervention and control groups of 8 kg) and assuming a standard deviation (SD) of weight loss of 5 kg, 65 participants per group provide greater than 90% power to detect a difference with each intervention arm and control. With this sample size, there will also be approximately 87% power to detect a difference between the combined intervention arm and each of the single intervention arms. These calculations assume a 20% missing rate at the end of Phase II and hypothesis testing done using the Holm p-value correction for multiple comparisons (more details provided below).

5.3 Specific Aim 4

Compare effectiveness of financial incentives and environmental strategies and combined arm during Phases I and II.

6. Secondary Outcome Variable(s)

Specific Aim 5

6.1 Compare the cost differences between each arm relative to the effectiveness measured by incremental weight loss achieved.

7. Study Instruments

7.1 Surveys/Assessments will be administered during various time points throughout the study via the online Way to Health (WTH) study platform

7.2 Medical history variables will be obtained as part of eligibility screening on the WTH study website.

7.3 Demographic measures will be collected at baseline (race, income, household size, education).

7.4 Physical Activity: The Global Physical Activity Questionnaire (GPAQ) measures adherence to national recommendations for moderate (30 minutes moderate physical activity 5 days per week) and vigorous (20 minutes continuous vigorous activity on 3 days per week) physical activity recommendations. This will be collected at 0, 6, 12, 18, and 24 months.

7.5 Dietary Behavior: The Food Intake 3 Factor Eating Questionnaire will be collected at months 0, 6, 12, and 18, and 24.

7.6 Stages of Change Model [Transtheoretical Model (TTM)], a commonly used measure of behavioral change which envisions the process of behavior change as stages through which an individual may progress, regress, or cycle as needed. This correlates with many types of health behaviors within different populations. This will be measured at 0, 6, 12, 18, and 24 months.

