All hypotheses will be tested using two-sided, 0.05-level tests unless otherwise specified (notably the Holm testing approach will be used for the five primary hypotheses in Specific Aims 1-4). The primary analyses will be an unadjusted intent-to-treat analyses, using a t-test for differences in weight change from baseline to 18 months, as measured by the in-person weight, between each intervention group and the control group, and the combined compared to each single intervention, applying the Holm p-value correction for multiple comparisons testing. If weight change appears to be non-normally distributed in the blinded data, we will find an appropriate. Missing data will be handled as described above.

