Weight change between baseline and 18 months, with 95% confidence intervals (CIs), will be estimated for comparison with adjusted analyses. We will estimate regression models adjusted for the stratification variables (sex, employer, initial BMI) and other participant characteristics factors including age, race, income, and education. We will evaluate the evidence of confounding for other baseline variables (baseline weight, marital status, household size, physical activities- i.e total minutes of MVPA+walking/week, eating behavior index, stages of change, SF-36 General Health) using change in estimate criterion (10%). We will fit exploratory models of the repeated weight measurements that incorporate time as a polynomial function or using visit-specific indicator variables to determine the most parsimonious model that adequately describes the observed patterns, as necessary. Models will be built separately for the in-person and at home weight data. Models using the at-home weight data would be considered only as potential exploratory analyses comparing the 3 intervention arms, since at-home weights are not available for the control arm. We will investigate random-effects models that allow for baseline individual variability as well as variability in the changes in weights over time; an example is the following: $E(\text{weight}_{ij}) = \beta_0 + \beta_1 \text{Time}_j + \beta_2 \text{Group}_i + \beta_3 X_i + b_{0i} + b_{1i} \text{Time}_j$, where i indicates subject, j indicates assessment times, the parameters are fixed effects linking time, a treatment group vector, and a vector of other demographic or clinical covariates X_i to the outcomes, and b_{0i} and b_{1i} are random intercept and slope effects. Tests for significance of random effects will use likelihood ratio tests for nested models; we will compare models with different random effects structures using the maximized log-likelihoods and the Akaike Information Criterion (AIC). We will apply standard diagnostic techniques to assess model adequacy. We will use treatment by time interactions to assess whether the rate of change in weight differs by intervention arm. We hypothesize that incentives may be more effective among lower income individuals and will evaluate this using interaction terms of income with treatment group. We will explore differential effects by race and education and baseline levels of intrinsic motivation and stages of change. We will also consider other potential mediators, such as the home food and activity environment. To assess the sensitivity of treatment effect estimates to missing

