11.2 Power and Sample Size Considerations

We have designed the study with adequate power to detect differences in weight loss over an 18-month period. Our intervention should achieve its maximal impact in maintaining initial weight loss at the end of Phase II (month 18), when the incentive payments cease. To maintain the experiment-wide Type I error and guard against false conclusions of effectiveness, we will use the Holm multiple comparisons adjustment for test the 5 primary comparisons in Specific Aims 1-4 . If the interventions are as effective as hypothesized, the proposed sample size maintains greater than 90% power to show significance for each of the three intervention arms compared to control and greater than 80% power to show significance for the combined intervention group compared to each of the two interventions alone.

It is important to note that while we originally planned to recruit 328 participants, a small subset was unable to successfully set up their Withings scales post randomization due to Wi-Fi connectivity issues. Therefore, we increased our target sample size by the number of people who were unable to connect their Withings scales to the Way To Health platform (16 additional subjects), bringing our recruitment total to 344 participants. The final statistical analysis is adjusted for the stratification factors to account for any imbalances that may have occurred. We have previously communicated this information to the IRB and the members of the Data Safety and Monitoring Board (DSMB), who approved this approach. The following information outlines our original power calculations and sample size considerations.

We plan to recruit approximately one third of the participants required for the start of Phase I from each of our participating employers (IBC, SEPTA, and City of Philadelphia). Given the large number of potentially eligible employees, we can, if needed, easily increase the proportion of participants from any of these employers to meet recruitment targets. Participants will be randomized to our 3 intervention groups and the control group using a 1:1 ratio for the intervention arms. We built in a margin of 20% of

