our original target sample size of 328 for potential attrition before the 18-month assessment, resulting in an expected 260 participants (65 per arm) who are available for analysis at the end of Phase II. This sample size will provide us with greater than 90% power to detect a difference in weight change between baseline and the 18-month weigh-in of 5 kg between each single intervention group and the control group (primary outcomes for Specific Aims 1-3) and 87% power to detect a 3 kg difference between the combined group and either the incentive or environmental strategies groups (Specific Aim 4). Namely, we will have greater than 85% power for the 5 primary comparisons of interest for an expected weight change between months 0-18 of -8 kg, -5 kg and 0 kg in the combined, intervention and control groups, respectively (a net difference between single intervention and control groups of 5 kg, combined intervention and control groups of 8 kg, and 3kg between the single interventions and combined group) and assuming a standard deviation (S.D.) of weight loss of 5 kg. We will also have greater than 80% power to detect a difference of 4.6 kg in weight change between single intervention and control groups and 7.3 kg between the combined and control groups (primary outcomes for Specific Aims 1-3), while maintaining approximately 80% power for a 2.7 kg difference between the combined and each single intervention (Specific Aim 4). For our secondary outcomes (Specific Aim 5), we wish to compare the cost differences between each arm relative to the effectiveness measured by incremental weight loss achieved. We will calculate a point estimate of cost per kg of weight loss based on estimated inter-arm differences in weight loss and the incremental cost of the interventions, as described in C.3.d.ii.c. For weight loss at 18 months, given an expected incremental cost of \$810 (incentives) and incremental weight loss of 5 kg, 328 participants provide 80% power to detect a cost per kg lost of \$430 and greater than 90% power to detect a cost per kg lost of \$575. This study is primarily a test of the efficacy of these interventions. Due to resource constraints and because we do not yet know about intervention effectiveness, we did not power this study based on cost effectiveness analyses. Estimated detectable costs per kg are a function of wide confidence intervals due to sample size.

11.3 Measurement of effect:

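### The supportive adjusted models leave baseline weight and six other baseline variables to a 10% change-in-estimate screen, so inclusion depends on chance imbalance relative to the observed effect rather than on prognostic value

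*Combined protocol and SAP*

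**What the plan says.** Section 11.1 (Efficacy Analyses) makes the primary test unadjusted: "The primary analyses will be an unadjusted intent-to-treat analyses, using a t-test for differences in weight change from baseline to 18 months". Five comparisons are tested with the Holm correction.

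The adjusted regressions come next, with the unadjusted estimates reported so that the two can be compared. One group of covariates is always included: "We will estimate regression models adjusted for the stratification variables (sex, employer, initial BMI) and other participant characteristics factors including age, race, income, and education". A second group is screened: "We will evaluate the evidence of confounding for other baseline variables (baseline weight, marital status, household size", together with physical activity, an eating behaviour index, stages of change and SF-36 general health. That makes seven variables, judged "using change in estimate criterion (10"%).

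The section does not say which of the five contrasts the 10% refers to, whether variables are screened singly or stepwise, or how the screen works across imputed data sets. The same seven variables already appear as predictors in the imputation model described under General procedures in section 11.1.

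Section 11.2 adds a different statement about adjustment: "The final statistical analysis is adjusted for the stratification factors to account for any imbalances that may have occurred". It names the stratification factors only.

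**The concern.** A change-in-estimate screen is a tool for finding confounders in observational data. Here the arms are formed by stratified permuted-block randomisation (section 10.3), so there is no systematic confounding to find. What the screen measures is the product of a covariate's prognostic strength and its chance imbalance, divided by the observed treatment effect. That denominator is the problem. For a given imbalance, a useful predictor tends to be left out when the effect is large, and an irrelevant variable can be let in when the effect is near zero.

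Baseline weight is collected on everyone and is a natural predictor of weight change, yet it is left to this screen. At stake are some precision in the adjusted estimates and their value as a check on the primary result, because their covariates are chosen partly by that result.

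**Working it through.** **Inputs.** From the documents: 65 per arm and SD 5 kg (section 5.2: "assuming a standard deviation (SD) of weight loss of 5 kg, 65 participants per group provide greater than 90% power"); effects of 5 and 8 kg against control (section 11.2: "a net difference between single intervention and control groups of 5 kg, combined intervention and control groups of 8 kg") and 3 kg for combined against a single intervention (section 11.2); two-sided testing (section 11.1: "All hypotheses will be tested using two-sided, 0.05-level tests unless otherwise specified"). Assumed: the correlation r between a screened covariate and weight change. The documents give none, so r = 0, 0.3 and 0.5 are shown.

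**Plan's own figure.** The standard error of a two-arm difference is 5 × √(2/65) = 0.877 kg. For 3 kg the noncentrality is 3/0.877 = 3.42. A two-sample t-test at two-sided α = 0.025 (a later Holm step) has 87.4% power, which matches the stated 87%. That calculation involves no covariates, so the 10% rule cannot affect it.

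**Algebra of the rule.** With the covariate in SD units, adjustment shifts the estimate by about r × 5 × d, where d is the difference in covariate means between arms. The covariate is kept if

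r × 5 × |d| ≥ 0.10 × |observed effect|.

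The standard error of d is √(2/65) = 0.175. At r = 0.3 and 5 kg, |d| must reach 0.5/1.5 = 0.33, or 1.90 standard errors, which has a chance of about 6%. At r = 0.5 and 5 kg, |d| must reach 0.5/2.5 = 0.20, or 1.14 standard errors, about 25%. Simulation also lets the observed effect and the slope vary.

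**Simulation.** Two arms of 65, SD 5 kg, one covariate, kept if the estimate changes by at least 10%. Runs of up to 20,000 trials per cell agree to within about a percentage point. Share of trials in which the covariate is kept:

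| r | 0 kg | 3 kg | 5 kg | 8 kg |
|---|---|---|---|---|
| 0 (pure noise) | about 34% | 2% | 0.1% | 0% |
| 0.3 | 78% | 27% | 9% | 1% |
| 0.5 | 89% | 50% | 25% | 8% |

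**Cost in precision.** SD of the estimate at a true effect of 5 kg, where the unadjusted value is 0.88 kg:

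| r | with the 10% rule | always adjusting |
|---|---|---|
| 0.3 | 0.87 | 0.84 to 0.85 |
| 0.5 | 0.80 | 0.76 |

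**Cost in power.** At 3 kg and α = 0.05, power with the rule against always adjusting is about 93.6% against 94.2% (r = 0.3) and 96.7% against 97.4% (r = 0.5). The unadjusted test has 92.4%. At 5 kg all are about 100%.

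**Type I error.** With no true effect, rejection at α = 0.05 under the rule was 4.1% to 5.0%.

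**If the rule were applied contrast by contrast.** With four arms at mean losses of 0, 5, 5 and 8 kg and 10,000 runs, the same single covariate was kept for some of the five contrasts and dropped for others in about 48% of trials (r = 0.3) and 79% (r = 0.5).

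**The case against.** The strongest reply is that nothing decisive depends on the rule. The primary analysis is the unadjusted t-test. Even if the section 11.2 sentence governed the final analysis, it names only stratification factors, and these are always included. A reader might infer that the screen threatens the primary p-values, the Holm procedure or the false-positive rate. The documents do not support that, and the simulated type I error is at or below nominal. This part of the reply stands in full.

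Second, the simulation compares one covariate with an unadjusted model, whereas the plan screens variables on top of seven that are always included. Initial BMI and sex probably carry part of the information in baseline weight, so the relevant r is a partial correlation, perhaps well below 0.5. This also stands: the precision figures are closer to upper values than to expected ones.

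Third, the always-included set, the candidate list and the threshold are all written down. A reader might call the adjusted analysis not pre-specified. That goes too far: the procedure is stated in advance, although the resulting covariate set depends on the data.

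Fourth, a reader might infer that each contrast will get its own covariates. The text does not say so. The one model it writes out, the repeated-measures example, carries all arms in a treatment group vector, which would give a single set. What remains is that the plan does not say which contrast the 10% refers to.

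Finally, section 11.1 speaks only of evaluating the evidence of confounding. That a variable then enters or stays out is the ordinary reading, not an explicit sentence. Keeping and dropping are tendencies, as the 50% at r = 0.5 and 3 kg shows.

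**Conclusion.** The concern holds for the supportive adjusted models, and it is minor. The 10% criterion makes the inclusion of baseline weight and six other variables depend on chance imbalance relative to the observed effect. At the 5 kg design effect, a covariate with r = 0.3 would be left out in about 91% of trials and one with r = 0.5 in about 75%. With no effect, pure noise would be let in about a third of the time.

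The loss is roughly 0.02 to 0.04 kg in the SD of the adjusted estimate and under one percentage point of power at 3 kg. In these settings the rule still gives precision and power no worse than the unadjusted test. The stronger reason to change it is that an adjusted analysis meant for comparison with the primary result should not choose its covariates by that result.

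These sizes rest on an assumed r, a single screened covariate, normal data and complete follow-up of 65 per arm. They shrink if initial BMI and sex already account for most of what baseline weight predicts.

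**What to change.** In section 11.1, delete the 10% change-in-estimate criterion. State one covariate set, fixed in advance, for the adjusted estimates of all five contrasts: employer, sex, baseline BMI stratum, age, race, income, education and baseline weight. Leave the other six screened variables in the imputation model, where section 11.1 already places them. A single set also removes the question of which contrast the 10% refers to. It would help to say in the same paragraph that these models are supportive and that the unadjusted t-test is primary, and to bring the section 11.2 sentence on stratification factors into line with that.

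The cost is SAP wording and about one degree of freedom for baseline weight. No new data, visits or participants are needed.

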11.2 Power and Sample Size Considerations

We have designed the study with adequate power to detect differences in weight loss over an 18-month period. Our intervention should achieve its maximal impact in maintaining initial weight loss at the end of Phase II (month 18), when the incentive payments cease. To maintain the experiment-wide Type I error and guard against false conclusions of effectiveness, we will use the Holm multiple comparisons adjustment for test the 5 primary comparisons in Specific Aims 1-4 . If the interventions are as effective as hypothesized, the proposed sample size maintains greater than 90% power to show significance for each of the three intervention arms compared to control and greater than 80% power to show significance for the combined intervention group compared to each of the two interventions alone.

It is important to note that while we originally planned to recruit 328 participants, a small subset was unable to successfully set up their Withings scales post randomization due to Wi-Fi connectivity issues. Therefore, we increased our target sample size by the number of people who were unable to connect their Withings scales to the Way To Health platform (16 additional subjects), bringing our recruitment total to 344 participants. The final statistical analysis is adjusted for the stratification factors to account for any imbalances that may have occurred. We have previously communicated this information to the IRB and the members of the Data Safety and Monitoring Board (DSMB), who approved this approach. The following information outlines our original power calculations and sample size considerations.

We plan to recruit approximately one third of the participants required for the start of Phase I from each of our participating employers (IBC, SEPTA, and City of Philadelphia). Given the large number of potentially eligible employees, we can, if needed, easily increase the proportion of participants from any of these employers to meet recruitment targets. Participants will be randomized to our 3 intervention groups and the control group using a 1:1 ratio for the intervention arms. We built in a margin of 20% of

our original target sample size of 328 for potential attrition before the 18-month assessment, resulting in an expected 260 participants (65 per arm) who are available for analysis at the end of Phase II. This sample size will provide us with greater than 90% power to detect a difference in weight change between baseline and the 18-month weigh-in of 5 kg between each single intervention group and the control group (primary outcomes for Specific Aims 1-3) and 87% power to detect a 3 kg difference between the combined group and either the incentive or environmental strategies groups (Specific Aim 4). Namely, we will have greater than 85% power for the 5 primary comparisons of interest for an expected weight change between months 0-18 of -8 kg, -5 kg and 0 kg in the combined, intervention and control groups, respectively (a net difference between single intervention and control groups of 5 kg, combined intervention and control groups of 8 kg, and 3kg between the single interventions and combined group) and assuming a standard deviation (S.D.) of weight loss of 5 kg. We will also have greater than 80% power to detect a difference of 4.6 kg in weight change between single intervention and control groups and 7.3 kg between the combined and control groups (primary outcomes for Specific Aims 1-3), while maintaining approximately 80% power for a 2.7 kg difference between the combined and each single intervention (Specific Aim 4). For our secondary outcomes (Specific Aim 5), we wish to compare the cost differences between each arm relative to the effectiveness measured by incremental weight loss achieved. We will calculate a point estimate of cost per kg of weight loss based on estimated inter-arm differences in weight loss and the incremental cost of the interventions, as described in C.3.d.ii.c. For weight loss at 18 months, given an expected incremental cost of \$810 (incentives) and incremental weight loss of 5 kg, 328 participants provide 80% power to detect a cost per kg lost of \$430 and greater than 90% power to detect a cost per kg lost of \$575. This study is primarily a test of the efficacy of these interventions. Due to resource constraints and because we do not yet know about intervention effectiveness, we did not power this study based on cost effectiveness analyses. Estimated detectable costs per kg are a function of wide confidence intervals due to sample size.

11.3 Measurement of effect:

The goal of this analysis will be to assess relative weight loss in the intervention arms relative to control. For the principal cost-effectiveness analysis, measurement of incremental weight loss will be based on differences in weight between baseline and the 18 month visit; in secondary analyses it will be based on weight differences between baseline and 24 months and baseline and 12 months.

12. Human Research Protection

